### **5.5.3 Handling of study treatment**

#### **5.5.3.1 Handling of investigational treatment**

Investigational treatment must be received by a designated person at the study site, handled and stored safely and properly, and kept in a secured location to which only the investigator and designees have access. Upon receipt, all investigational treatment should be stored in a

refrigerator according to the instructions specified on the labels. Clinical supplies are to be dispensed only in accordance with the protocol.

[figure not shown]
Medication labels will be in the local language and comply with the legal requirements of each country. They will include storage conditions for the drug and no information about the patient.

Unblinding will only occur in the case of patient emergencies (see [Section 5.5.10](#)), at the time of the predefined interim efficacy analyses, and at the conclusion of the study. The investigator must maintain an accurate record of the shipment and dispensing of investigational treatment in a drug accountability log. Monitoring of drug accountability will be performed by the field monitor during site visits and at the completion of the trial. At the conclusion of the study, and as appropriate during the course of the study, the investigator will return all unused investigational treatment, packaging, drug labels, and a copy of the completed drug accountability log to the Novartis monitor or to the Novartis address provided in the investigator folder at each site.

[figure not shown]
#### **5.5.4 Instructions for prescribing and taking study treatment**

The study drug infusion will begin after the signing the ICF and the completion of all screening procedures, and continue for 48 hours. Study drug should be administered in a dedicated IV line or port, as soon as possible, but no more than 4 hours after randomization. Serelaxin infusion solution must be prepared in infusion bags containing 5% dextrose as a diluent. Recommended infusion bags, which have been tested and qualified for use with serelaxin, are listed in [Table 5-1](#).

However, there is no restriction for use of any other 250 mL infusion bag with 5% dextrose.

Compatible infusion filters, which have been tested and qualified for use with serelaxin, **must** be used to administer the study drug. [Table 5-2](#) lists the infusion filters that can be used for this study.

For each randomized patient to receive the study drug according to a weight-range adjusted dosing regimen over a period of 24 hours ([Table 5-3](#)), the required amount of study drug will be withdrawn from the 6-mL vials (with 3.5 mL fill) contained in the blinded kits, taking care not to shake the vial, injected into a 250 mL intravenous bag of 5% dextrose solution recommended above, and then infused at a constant rate of 10 mL/hour. Details of study drug preparation and infusion can be found in the *Pharmacy Manual*.

Study drug will be dispensed only by study staff qualified to perform that function under applicable local laws and regulations for the study site(s), according to the protocol and Schedule of Events (see [Table 6-1](#)). The blinded study drug kits, allocated to each randomized patient via IRT, containing one 6-mL vial of serelaxin or placebo (with 3.5 mL fill), will be used to compound study drug for the first 24 hour of infusion for all patients <115 kg in weight; in cases when the subject is  $\geq$ 115 kg, two study drug kits will be assigned via IRT for the first 24 hour of infusion. The body weight determined between presentation and randomization, rounded up to the nearest 0.5 kg, will be used for the calculation of the dose for each patient, for the entire 48 hour infusion period. Study drug from a second kit or pair of kits, also assigned via IRT depending on the patient's body weight as assessed between presentation and randomization, will be used to continue the infusion for the second 24 hours.

**Table 5-3 Weight-range adjusted dosing regimen of serelaxin (or placebo)**

Body weight (kg)	Serelaxin or placebo (mg)	Volume of serelaxin or placebo to be added to 250 mL IV bag of sterile 5% dextrose for intravenous infusion over a period of 24 hours
40-59 kg	2.0 mg	2.0 mL
60-74 kg	3.0 mg	3.0 mL
75-114 kg	3.5 mg	3.5 mL
115-160 kg	5.5 mg	5.5 mL (2 vials needed)

All kits of investigational treatment assigned by the IRT will be recorded/databased in the IRT.

### 5.5.5 Permitted dose adjustments and interruptions of study treatment

[Table 5-4](#) describes the actions required for a systolic BP decrease during the period of study drug infusion, which must be strictly followed.

**Table 5-4 Dosing adjustment of study drug administration in the event of systolic BP decrease**

Changes in systolic BP during infusion*	Adjustments of study drug administration
Decrease >40 mmHg from pre-treatment at baseline, but systolic BP remains $\geq$ 100 mmHg	Reduce the infusion rate by half for the remainder of the study drug administration, i.e., reduce infusion rate from 10 mL/hour to 5 mL/hour for the remainder of 48-hour infusion
Decrease in absolute systolic BP to <100 mmHg	Permanently terminate study drug infusion

\* These systolic BP values should be confirmed by two measurements taken 15 minutes apart

In addition, dosing may be discontinued at any time at the discretion of the investigator. Reasons the investigator may discontinue study drug administration include, but are not limited to, serious or intolerable AEs suspected to be related to study drug. If dosing is discontinued for systolic BP decreases, or any safety reasons, it should not be restarted. Re-administration of study drug once terminated for safety reasons is not allowed. The total time from initiation of study drug infusion to completion must not exceed 48 hours. In the event that study drug administration is discontinued, regardless of the reason, the patient will continue to be followed at all study visits defined in the protocol.

Changes in study drug dose must be recorded on the Dosage Administration Record CRF.

### **5.5.6 Rescue medication**

The investigator may prescribe any medications and/or supportive care during the study based on clinical needs. Any medication and/or supportive care administered must be recorded on the appropriate Concomitant Medications or Tests/Procedures/Treatments CRFs.

### **5.5.7 Concomitant treatment**

To be eligible for the study, all patients must have received IV furosemide of at least 40 mg (or equivalent) at any time between presentation to emergency services (this includes outpatient clinic, ambulance, or hospital including emergency department) or hospital and screening for the study.

Patients will not be enrolled in the study if concomitant therapy for AHF includes current (within 2 hours prior to randomization) or planned (through the completion of study drug infusion) treatment with any cardiovascular IV therapies, including vasodilators (including nesiritide), positive inotropic agents and vasopressors, or mechanical support (intra-aortic balloon pump, endotracheal intubation, mechanical ventilation, or any ventricular assist device), with the exception of IV furosemide (or equivalent), or IV nitrates at a dose of  $\leq 0.1$  mg/kg/hr if the patient has a systolic BP  $> 150$  mmHg at screening. Use of IV furosemide (40 mg or equivalent) is an inclusion criterion; further doses of IV furosemide can be administered at any time after enrollment.

Major cardiovascular and non-cardiovascular classes of medication taken by a subject approximately 30 days prior to study drug initiation and on a daily basis while hospitalized through Day 5, at Discharge, and at Days 14, 60, 120 and 180 will be recorded. Only those medications currently being taken or that were taken within 24 hours prior to the visit will be collected. These include but are not limited to: loop diuretics, other diuretics, ACE inhibitors, angiotensin receptor antagonists, beta-blocker, hydralazine, nitrates, calcium channel blockers, digoxin, non-steroidal anti-inflammatory agents, COX-2 inhibitors, aminoglycoside antibiotics, inotropes, vasodilators and others (e.g. insulin, oral antidiabetics, statins, anticoagulants etc.).

The investigator may prescribe any additional medications during the study as dictated by the patients' condition. Administration of standard treatment should in no instance be delayed or withheld due to patient's participation in the study. Standard treatment includes, but is not limited to, administration of the major classes of medications, as described above, as well as administration of oxygen, analgesics, anxiolytics and sedatives, as needed.

Heart failure medications, procedures and significant non-drug therapies administered after the patient was enrolled into the study must be recorded. The investigator should instruct the patient to notify the investigator or associated study personnel about any new medications he/she takes after the patient was enrolled into the study.

### **5.5.8 Prohibited Treatment**

Use of IV vasoactive therapies within 2 hours prior to randomization is an exclusion criterion with the exception of IV loop diuretics, or IV nitrates at a dose of  $\leq 0.1$  mg/kg/hour if the patient has a systolic BP  $>150$  mmHg at screening. Thus, study drug should be started concomitantly with IV nitrates only if at a low dose ( $\leq 0.1$  mg/kg/hour) in a patient with high systolic BP ( $>150$  mmHg).

Post-randomization, the investigator may prescribe any additional medication as dictated by the patients' condition. Administration of standard treatment should never be delayed or withheld due to patient's participation in the study. The investigator should exercise caution when up-titrating or adding concomitant standard therapies that might decrease BP during study drug infusion. Investigator may consider not administering all BP lowering medication simultaneously. Changes to these medications during the index hospitalization should be recorded on the CRF.

### 5.5.9 Discontinuation of study treatment and premature patient withdrawal

**Discontinuation of study treatment:** The investigator should discontinue the study drug infusion for a patient if, on balance, he/she believes that continuation would be detrimental to the patient's well-being. In particular, the study drug administration must be discontinued under the following circumstances:

- If the patient's systolic BP falls to <100 mmHg in two consecutive measurements 15 min apart, study drug must be permanently discontinued. Measures may be taken by the investigator to address the decrease in blood pressure during the intervening 15 minutes, if clinically indicated. (see details in [Table 5-4](#))
- Pregnancy
- Any significant risk to the patient's safety

Patients who discontinue study treatment should NOT be considered withdrawn from the study. They should be followed per the visit/assessment schedule illustrated in [Table 6-1](#) until the study is complete. If they fail to return for these assessments for unknown reasons, every effort should be made to contact them as specified in [Section 5.5.11](#).

For any patient(s) whose treatment code has been broken inadvertently for any reason, study drug treatment should be continued.

**Patient withdrawal:** Patients may voluntarily withdraw consent to participate in the study for any reason at any time.

Withdrawal of consent occurs only when a patient does not want to participate in the study anymore and, does not want any further visits or assessments and, does not want any further study related contacts and does not allow analysis of already obtained biologic material.

If a patient withdraws consent, the investigator must make every effort to determine the primary reason for this decision and record this information. Study treatment must be discontinued and no further assessments conducted. All biological material that has not been analyzed at the time of withdrawal must not be used. Further attempts to contact the patient are not allowed unless safety findings require communicating or follow-up. However, if local regulations permit, sites will be asked to check public registries on a regular basis to try and obtain a health status on their patients, so that the Survival Information eCRF page can be completed.

Patients can also refuse to participate in specific aspects of the study and/or take study medication at any time without withdrawing consent and permission should be requested of the patient to conduct follow-up visits or calls. Investigators should make every effort to accommodate the needs of the patients to make it possible for them to continue to participate in the remaining aspects of the study. This includes performing telephone visits to obtain health status and/or mortality information for patients who are unable to or refuse to return for clinic visits.

**Lost to follow-up:** For patients whose status is unclear because they fail to appear for study visits without stating an intention to withdraw, the investigator should show "due diligence" by contacting the patient, family or family physician as agreed in the informed consent and by documenting in the source documents steps taken to contact the patient, e.g. dates of telephone calls, registered letters, etc. A patient should not be considered lost to follow-up until just prior to database lock, after every effort to contact the patient has been exhausted.

#### **5.5.10 Emergency breaking of treatment assignment**

Emergency treatment code breaks should only be undertaken when it is essential to treat the patient safely and efficaciously. Most often, study treatment discontinuation and knowledge of the possible treatment assignments are sufficient to treat a study patient who presents with an emergency condition. Currently, there is no known treatment available to reverse the effect of seralaxin. Consequently, in case of an emergency, management of the emergency condition will be independent from the knowledge of study treatment. If the knowledge of study treatment is deemed absolutely necessary, emergency treatment code breaks will be performed using the IRT. When the investigator contacts the system to break a treatment code for a patient, he/she must provide the requested patient identifying information and confirm the necessity to break the treatment code for the patient. The investigator will then receive details of the investigational drug treatment for the specified patient and a fax or email confirming this information. The system will automatically inform the Novartis monitor for the site and the Global Trial Leader (GTL) that the code has been broken.

It is the investigator's responsibility to ensure that there is a procedure in place to allow access to the IRT in case of emergency. The investigator will inform the patient how to contact his/her backup in cases of emergency when he/she is unavailable. The investigator will provide protocol number, study treatment name, patient number, and instructions for contacting the local Novartis CPO (or any entity to which it has delegated responsibility for emergency code breaks) to the patient in case an emergency treatment code break is required at a time when the investigator and backup are unavailable.

Any patient who is unblinded will continue in the study and complete all study assessments according to the protocol.

#### **5.5.11 Study completion and post-study treatment**

Patient participation will be completed 180 days after the start of the study drug infusion.

The investigator also must provide follow-up medical care for all patients who are prematurely withdrawn from the study, or must refer them for appropriate ongoing care.

#### **5.5.12 Early study termination**

The study can be terminated at any time for any reason by Novartis. Should this be necessary, the patient should be seen as soon as possible and treated for a prematurely withdrawn patient. The investigator may be informed of additional procedures to be followed in order to ensure that adequate consideration is given to the protection of the patient's interests. The investigator will be responsible for informing IRBs and/or ECs of the early termination of the trial.

It is planned to have one formal interim efficacy analyses. The cut-off for this interim analysis is planned when 60% of the targeted total number of CV deaths is achieved. The trial may be

concluded early for efficacy, at the recommendation of the DMC, if a significant difference between two treatment arms for the number of CV deaths is achieved by crossing the pre-specified boundary at interim analysis.

## 6 Visit schedule and assessments

Table 6-1 lists all of the assessments and indicates with an “X” or “S” when the required assessments and/or procedures are performed at a scheduled study visit. Patients should be seen for all visits on the designated day or timepoint, or as close to it as possible. Patients are expected to return to the clinic for all scheduled outpatient study visits. Patients unable or unwilling to return to the hospital/clinic for scheduled outpatient visits will be contacted by telephone as close as possible to the expected visit to obtain information about endpoints and survival status.

Patients who prematurely discontinue the investigational treatment remain in the study and should undergo all the assessments illustrated in Table 6-1. If a patient withdraws from participation in the study, refuses to return for study assessments or is unable to do so, every effort should be made to contact them or a knowledgeable informant by telephone and/or other measures to determine the patient’s survival status during the follow-up period.

Patients eligible to participate in this study must be randomized within 16 hours of presentation. Presentation starts at the earliest of (1) time of presentation either at the ER/ED, ICU/CCU or ward, (excludes EMS or other pre-hospital care); or (2) time of first IV loop diuretic prior to arrival at the hospital (this includes outpatient clinic, ambulance, or hospital including emergency department) for the current AHF episode.

Prospective study candidates will be identified either enroute to or upon arriving at the ED/ER/hospital. After identifying a potential subject, an ICF must be signed before performing study-related screening procedures that are not considered standard of care for AHF patients at that site. Procedures that are part of a site’s standard of care for an individual with AHF may pre-date the signed ICF. The AE and SAE reporting period will begin at the time the ICF is signed.

Screening will continue until the patient has been deemed eligible for enrollment and randomized into the study via the IRT.

Epoch	Screening	Randomized Treatment												
	Screen d	Baseline	Study drug infusion a					Post-treatment daily assessments				Follow-up c		
Time points	Hour -16	Hour 0 (Day 1)	Hour 6 (Day 1)	Hour 12 (Day 1)	Hour 24 (Day 1)	Hour 48 (Day 2)	Hour 72 (Day 3)	Hour 96 (Day 4)	Hour 120 (Day 5) b	Discharge e	Day 14	Day 60	Day 120	Day 180 /PSW
Visits	1	101	102	103	104	105	106	107	108		109	110	111	199
Assessment of readmission											X	X	X	X
Administer study medication		X												
Contact IRT/IWRS		X			X									
Adverse and serious adverse events m		X			X	X	X	X	X	X	X			
Follow up completion form														X
Withdrawal of Informed Consent Form p	X													X

PSW = premature patient withdrawal; X= assessment to be recorded on clinical database; S= assessment to be recorded on source documentation

a Study drug treatment will be administered as continuous intravenous infusion for up to 48 hours. Dosage can be adjusted under specific circumstances as described in [Section 5.5.5](#)

b Patients discharged prior to Day 5 will return to the hospital/clinic for Day 5 procedures. Patients unable or unwilling to return to the hospital/clinic will be contacted on or after Day 5 by telephone to obtain information about AEs/SAEs, potential endpoints and survival status.

c Patients discharged prior to Day 14 will return to the hospital/clinic for Day 14 procedures. Patients unable or unwilling to return to the hospital/clinic will be contacted on or after Day 14 by telephone to obtain information about SAEs, potential endpoints and survival status. The Day 60 and Day 180 assessments will be conducted as outpatient visits if the patient is discharged prior. The Day 180 assessments can be performed as early as - 7 days from the timepoint. The Day 120 assessment will be conducted by telephone. Patients unable or unwilling to return to the hospital/clinic for scheduled outpatient visits will be contacted by telephone as close as possible to the expected visit to obtain information about endpoints and survival status. If a patient fails to return for the remaining outpatient visit(s) the investigator should show “due diligence” by contacting the patient, family or family physician up to the time of database lock.

d Procedures performed as part of a site’s standard of care for an individual with AHF can be done during the pre-screening interval and may pre-date the signed ICF.

e If Discharge Visit coincides with a scheduled visit, only the Discharge Visit will be performed.

f At screening, a locally-analyzed sample will be obtained for female patients of child-bearing potential to qualify the patient for study entry.

g Chest X-ray may be interpreted by the study physicians or physicians attending to the patient. Interpretation and the person interpreting the radiograph must be recorded in the source documentation. A radiologist’s interpretation is not necessary for the purposes of the study.

h A complete physical will be performed at screening; an abbreviated physical examination will be performed at all other specified timepoints. Following randomization, all physical examinations should be performed daily at approximately the same time of day. Daily vital signs measurements may be made and recorded by trained study personnel as well as trained healthcare personnel as part of their routine clinical duties. The first recorded measurement per day will be used as the daily measurement for that day. Refer to [Section 6.5.1](#).

 BP and HR measurements are to be performed at 30 & 60 minutes and then every hour for the first 6 hours of study drug infusion, and then every 3 hours during study drug infusion, including night time hours. Post-infusion, BP and HR are to be measured every 3 hours until 12 hours following end of infusion, then every 6 hours for 48 hours and then every 24 hours until the earlier of Day 5 or Discharge. All measurements should be performed as close as possible to specified timepoints. BP and HR are to be measured with the patient in the same position and with the same equipment using the same arm, throughout study drug infusion. These measurements may be made and recorded by trained healthcare personnel as part of their routine clinical duties, as well as trained study personnel. Refer to [Section 6.5.2](#).

j Blood will be locally collected and analyzed daily during hospitalization. If discharge occurs prior to Day 5, local blood collection will not be required at the Day 5 hospital/clinic visit. Following randomization, local laboratory collections can be adjusted to conform to the hospital's routine laboratory collection schedule and can be collected at any time of day. Refer to [Section 6.5.4](#).

k Blood will be collected in a subset of randomized patients participating in the laboratory substudy for measurement of biochemistry, hematology, and plasma HbA1C by the central laboratory. Following randomization, central laboratory collections can be adjusted to conform to the hospital's routine laboratory collection schedule and can be collected at any time of day. Baseline collection can be done at screening at the same time as the local laboratory collections. Urine dipstick will be measured locally at screening to rule out any conditions requiring further diagnostic evaluation or treatment. Refer to [Section 6.5.4.3](#)

l Blood will be collected in a subset of randomized patients participating in the biomarker substudy to be performed by the central laboratory. Following randomization, biomarker substudy laboratory collections can be adjusted to conform to the hospital's routine laboratory collection schedule and can be collected at any time of day. Refer to [Section 6.6.6](#)

m Non-serious AEs and SAEs will be reported from the signing of the ICF through Day 5 and 14, respectively.

n ECGs will be collected in a subset of randomized patients participating in the ECG substudy and sent to a central ECG vendor for evaluation. ECGs will be collected at Baseline and at the end of study drug infusion. Refer to [Section 6.5.5](#).

o Major cardiovascular and non-cardiovascular classes of medication taken by a subject approximately 30 days prior to study drug initiation and on a daily basis while hospitalized through Day 5, at Discharge, and at Days 14, 60, 120 and 180 will be recorded. Only those medications currently being taken or that were taken within 24 hours prior to the visit will be collected.

p Withdrawal of consent form is only completed when a patient does not want to participate in the study any more and, does not want any further visits or assessments and, does not want any further study related contacts and does not allow analysis of already obtained biologic material..

q ECGs will be performed and interpreted locally at screening and at Day 5 or discharge, whichever occurs first. The ECG interpretation and person interpreting the ECG must be recorded in the source documents

r The echocardiogram should be performed as soon as possible post randomization, but prior to discharge. If an echocardiogram is performed during the screening period (i.e. within the 16 hours window) and the patient is subsequently randomized, the screening echocardiogram will qualify as the index hospitalization echocardiogram and a repeat echocardiogram post randomization will not be necessary.

s At hours 24, 48, 72, 96 and 120, physician assessment of HF signs and symptoms will include an assessment of the occurrence of worsening heart failure in the interval preceding the visit. These evaluations should be done at approximately the same time of day, each day, in the same position, and hospital/clinic setting, preferably by the same assessor. Refer to [Section 6.4.4](#).

t Body weight measurements performed during hospitalization can be performed anytime

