## 14 Appendix 1: Clinically notable laboratory values

Clinically notable laboratory abnormalities for selected tests based on a percent change from baseline (screening laboratory):

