The CRLX030A2301 study (also referred to as RELAX-AHF-2) aims to evaluate the efficacy, safety and tolerability of intravenous infusion of 30 µg/kg/day serelaxin for 48 hours, when added to standard therapy. Data from this study is intended to replicate the reduction in mortality in AHF patients observed in the RELAX-AHF study.

The purpose of this document is to outline the planned analyses to be completed to support the completion of the Clinical Study Report (CSR) for RELAX AHF-2.

2 Statistical methods planned in the protocol and determination of sample size

Data will be analyzed according to the data analysis section 10 of the study protocol which is available in [Appendix 16.1.1 of the CSR](#).

All nominal time points will be used for analysis; actual assessment times will not be used to reclassify the time point at which a measure was taken. Time-to-event analyses will be based on actual dates (time) reported.

All references to index hospitalization refer to the initial hospitalization for AHF.

Unless specified, descriptive statistics indicates mean, median, standard deviation, minimum and maximum will be presented for continuous variables; the number and percentage of subjects in each category will be presented for categorical variables for each treatment group and all subjects (total).

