2.1.3 Visit, baseline and post baseline definitions

Except for biomarkers (described in Section 2.2.7.3), discharge visit will be mapped to Day 1, 2, 3, 4, 5, 14 (with +/- 3 day window), 60 (with +/- 7 days window), 120 (with +/- 7 days window), 180 (with +/- 7 day window) if the scheduled visits are missing.

Screening phase: The screening phase is defined as the period prior to randomization. After obtaining written informed consent, the subject will be evaluated for eligibility to participate in to the study.

Baseline definition for efficacy/safety measurements: Baseline is defined as Hour 0/Day 1 assessment. The baseline date and time will be considered the date and time of initiation of study drug, or randomization if the subject was not treated with study drug. If missing, the value at screening visit will be used.

Post-baseline phase for efficacy/safety measurements: The post-baseline phase begins at the time when study drug administration starts (Hour 0/Day 1) and ends with the last study assessment/last follow-up or the death of subject. For subjects who did not receive study drug, the phase begins at time of randomization.

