2.3.4 Electrocardiogram (ECG)

An ECG substudy will be conducted at a subset of selected sites to enroll at least 500 subjects. Subjects without written informed consent for the ECG substudy before any study-specific assessment is performed will be excluded from the population.

The analyses will be performed based on subjects who have at least one ECG at baseline (ECG recordings taken before the infusion starts will be considered) and one ECG post baseline (48 hour time point) which is recorded within 60 minutes after study drug infusion ends.

The following quantitative variables will be summarized: RR interval, PR interval, QRS duration, QT interval, and corrected QT interval (QTc).

The number and percentage of subjects with the following criterion will be presented.

- QT > 500 msec
- QT > 480 msec
- QT > 450 msec
- QT > 450 msec, male only
- QT > 460 msec, female only
- QT increases from baseline > 30 msec
- QT increases from baseline > 60 msec
- PR > 200
- PR > 220 msec
- PR increases from baseline > 25%
- QRS > 110 msec and increase from baseline $\geq 25\%$
- QRS > 120 msec and increase from baseline $\geq 25\%$
- Heart rate > 100 beats per minute and increase from baseline $\geq 25\%$
- Heart rate < 50 beats per minute and decrease from baseline $\geq 25\%$

QT data will be analyzed for both the Fridericia (primary) and Bazett's (secondary) corrections.

Newly occurring abnormalities in ECG morphology will be summarized by treatment group and overall. Newly occurring is defined as no occurrence on any of the baseline ECGs with the presence of the finding on any single ECG post baseline.

A listing of all abnormalities will be provided, as well as a by-subject listing of all quantitative ECG parameters.

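### A biomarker or central-laboratory sample labelled baseline but drawn after infusion start would be kept as baseline, because no rule compares its time with the infusion

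*Protocol*

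**What the plan says.** **Sampling.** Protocol 5.3 places randomization at the baseline visit. Protocol 5.5.4 has the infusion start as soon as possible and within 4 hours of randomization, once consent and the screening procedures are complete; baseline samples are not named as a precondition. Footnotes k (central laboratory) and l (biomarkers) of Table 6-1 say that, following randomization, collections may be fitted to the hospital's "routine laboratory collection schedule and can be collected at any time of day". Footnote k adds, for the central laboratory, "Baseline collection can be done at screening at the same time as the local laboratory collections". This is an option and not a requirement, and footnote l has no counterpart for biomarkers. Protocol 3.1 schedules biomarkers at Baseline, Days 2 and 5, Discharge and Day 14.

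**Analysis.** SAP 2.1.3 states "Baseline is defined as Hour 0/Day 1 assessment", with the screening value used only when that one is missing. The same section sets the baseline date and time at initiation of study drug (randomization if untreated) and starts the post-baseline phase there. The opening of SAP 2 says "actual assessment times will not be used to reclassify the time point at which a measure was taken". SAP 2.2.7.3 fits log-baseline as a covariate, with a visit-by-baseline interaction, in the biomarker model.

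**Contrast.** For the ECG baseline, SAP 2.3.4 specifies "ECG recordings taken before the infusion starts will be considered". Protocol Appendix 1 defines notable laboratory values "based on a percent change from baseline (screening laboratory" values).

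**The concern.** Baseline should be untouched by treatment. If some baseline samples are drawn during the infusion, the baseline value becomes partly an outcome. In the biomarker model, adjusting for a covariate the drug has already moved removes part of the effect being estimated. In the central-laboratory summaries and shift tables, and in the creatinine and eGFR threshold counts of SAP 2.3.2.2 as applied to central data, early movement would be absorbed into baseline and not counted as change. At stake are one other-secondary efficacy endpoint and the central-laboratory safety description.

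**Working it through.** No figure in the plan depends on this point, so there is none to reproduce. The check is a comparison of rules, followed by an illustration.

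**Step 1: can a late draw be labelled baseline?** Take a biomarker-substudy patient who is randomized, starts the infusion within the permitted 4 hours, and has the baseline sample taken at the next routine collection round, after the infusion has started.

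- Footnote l allows a draw after randomization at whatever hour the hospital's routine dictates.
- Protocol 5.5.4 does not hold the infusion for the sample.
- The next scheduled biomarker sample is Day 2, so the only nominal slot for this draw is Baseline.

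The same holds for a central-laboratory baseline sample that was not taken at screening.

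**Step 2: what does the SAP do with it?**

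| Rule | Status of the late sample |
|---|---|
| SAP 2.1.3, baseline is the Hour 0/Day 1 value | Baseline, by label |
| SAP 2.1.3, screening used only if that value is missing | Not triggered, since a value exists |
| SAP 2, actual times do not reclassify | Stays baseline |
| SAP 2.1.3, post-baseline phase begins with the infusion | Post-baseline, by time |

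Three rules keep the value as baseline and one contradicts them. The only sentence that says what to do when label and clock time disagree is the one in SAP 2, and it favours the label.

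**Step 3: illustrative size.** Let *D* be the true treatment effect on the log biomarker at a given visit, *p* the share of baselines drawn after infusion start, *r* the share of *D* already present at such a draw, and *s* the slope of log follow-up on log baseline. Then:

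- difference in mean baseline between arms = *p* × *r* × *D*
- adjusted effect = *D* − *s* × (*p* × *r* × *D*) = *D*(1 − *p r s*)
- proportion lost = *p r s*; for an unadjusted change from baseline, *s* = 1

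None of *p*, *r* and *s* is in the documents. Assuming 10% to 50% for *p* and *r*, and a slope of 0.5 or 0.7:

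| *p* = *r* | *s* = 0.5 | *s* = 0.7 | Change score (*s* = 1) |
|---|---|---|---|
| 10% | 0.1 × 0.1 × 0.5 = 0.5% | 0.7% | 1% |
| 25% | 0.25 × 0.25 × 0.5 = 3.1% | 4.4% | 6.25% |
| 50% | 0.5 × 0.5 × 0.5 = 12.5% | 17.5% | 25% |

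The loss is towards no difference provided the early effect has the same sign as the later one.

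**The case against.** The best defence is that the plan's intent is plainly pre-dose. SAP 2.1.3 dates baseline at drug initiation, Protocol Table 5-4 speaks of baseline as pre-treatment, and Protocol 6 asks for visits at the designated timepoint or as close to it as possible. The footnotes can be read as relaxing the clock hour, not the order of draw and infusion, and the only flexibility stated for the central-laboratory baseline is towards an earlier draw. A timing rule may also exist in the separate biomarker analysis plan, the substudy protocol or the laboratory manual, none of which was available.

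The intent is clear, but intent does not reclassify a value. A draw as close as possible to Hour 0 may fall on either side of it, and SAP 2 then keeps the label. The ECG section shows that a pre-infusion condition was written where it was thought necessary.

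The objection does succeed against several broader readings that a reader might infer:

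- **Any Day 1 value can become baseline.** Not supported. Hours 0, 6, 12 and 24 are separate visits (101 to 104), and baseline is Hour 0.
- **Weight is affected.** Not shown. A footnote says "Body weight measurements performed during hospitalization can be performed anytime", but Protocol 6.5.3 lists Screening and Days 1-5 with no baseline weight. If no Hour 0 weight exists, the SAP falls back to screening. The weight and laboratory rows of Table 6-1 could not be read in the text reviewed.
- **Local laboratory results are affected.** Footnote j has similar wording ("Following randomization, local laboratory collections can be adjusted to conform to the hospital's routine laboratory collection schedule"), but Protocol 6.5.4 lists screening and daily samples with no separate baseline draw, and notable values use the screening laboratory.
- **Vital signs are affected.** Their baseline is scheduled separately from the infusion measurements in Protocol 6.5.2, and no timing problem appears.

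**Conclusion.** The point holds as a gap in the rules, for biomarker samples and for central-laboratory samples not drawn at screening. As written, the plan would keep a sample labelled baseline but taken after infusion start, against the SAP's own definition of the post-baseline phase.

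The documents do not say how many samples this would touch, and it should not be inferred that late baselines are common. The range in the working (0.5% to 17.5% with baseline as covariate, 1% to 25% for a change score) reflects assumed inputs and is not an estimate of bias in this trial.

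The logrank test of CV death, the Gehan-Wilcoxon test of WHF and the key secondary tests use no baseline value and are unaffected. The biomarker endpoint carries no multiplicity adjustment. The point therefore merits correction before unblinding, but does not threaten the trial's main conclusions.

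**What to change.** In SAP 2.1.3, define baseline for biomarker and laboratory variables as the last non-missing value whose recorded date and time precede infusion start (randomization if untreated), screening samples included. Apply the same rule to weight if a Day 1 weight is to serve as baseline. State that a value labelled Hour 0/Day 1 but timed after infusion start is not used as baseline, and exempt this rule from the nominal-time sentence in SAP 2. Because local and central results are presented separately, say that the baseline must come from the same laboratory source as the follow-up values. In protocol footnotes k and l, exempt the baseline draw from the time-of-day flexibility. The separate biomarker analysis plan should carry the same definition.

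The cost is a few sentences and one date/time comparison in programming. The downside is that a few substudy patients with no pre-infusion sample would have no baseline for the change analysis; their number should be reported by arm. A count of baseline samples timed after infusion start would also show whether the issue mattered in practice.
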